## ABSTRACT

In the United States, patients dependent upon parenteral nutrition (PN) receive parenteral fat emulsions composed of soybean oils. Lipids are necessary in PN-dependent patients due to their high caloric value and essential fatty acid content. They have been implicated in predisposing patients to PN-associated liver disease, and children requiring prolonged courses of PN are at risk for developing PN-associated liver disease. Animal studies have shown that IV fat emulsions such as fish oil that are high in eicosapentaenic and docosahexaenoic acid reduce impairment of bile flow which is seen in cholestasis caused by conventional fat emulsions. We hypothesize that a fat emulsion comprised of omega-3 fatty acids (i.e., fish oil) such as Omegaven™ will be well tolerated and will reduce the inflammatory effect in the liver of prolonged PN exposure, with the potential of reversing any hepatic dysfunction due to PN/IFE use. By administering Omegaven™ in place of conventional phytosterol/soybean fat emulsions we may reverse or prevent the progression of PN associated cholestasis and thus allow the patient to be maintained on PN until they are able to ingest adequate nutrition enterally.

All patients in the Intestinal Rehabilitation Program at UNMC with an abnormal serum bilirubin (>2mg/dL), receiving PN and not meeting an exclusion criteria will be approached for enrollment. Upon enrollment, the PN lipid source will be switched to Omegaven, and patients will continue to be followed in standard fashion for ongoing intestinal rehabilitation. Patients will continue to have regular follow-up including laboratory evaluation at least once weekly, with periodic radiologic and endoscopic evaluation as per our standard of care. As hypertriglyceridemia is a possible side effect of Omegaven, weekly triglyceride levels will be added to regular labs. Patients will be continued on Omegaven until weaned from intravenous lipids per standard of care. Clinical data will be collected prospectively and will be compared with historical controls.

## BACKGROUND AND RATIONALE

Patients with intestinal failure are unable to support growth or maintain health without some provision of nutrition parenterally. The Intestinal Rehabilitation Program at the University of Nebraska Medical Center is a multidisciplinary team focused on achieving enteral nutritional independence through optimization of intestinal function and autologous reconstruction of the GI tract. The program functions, along with small bowel transplantation, as part of the comprehensive intestinal failure program at UNMC. Many of our patients have excellent bowel rehabilitation potential given sufficient time for reconstruction and intestinal adaptation, but are limited by concurrent progression of parenteral nutrition-associated liver disease (PNALD). The ability to slow or reverse PNALD may dramatically impact on our ability to treat intestinal failure.

Lipids are necessary in PN dependent patients due to their high caloric value and essential fatty acid content. In the United States, most patients dependent upon PN receive parenteral fat emulsions composed of soybean oils, which have been implicated in predisposing patients to PN-associated liver disease (PNALD). There is evidence in the scientific literature supporting use of lipid formulations comprised mainly of omega-3 fatty acids to halt or reverse the progression of PNALD (Gura, 2008; Diamond, 2009). It is believed that fish oil-based formulations such as Omegaven™ mediate reduction of liver injury through inhibition of de novo lipogenesis, reduction of arachidonic acid-derived inflammatory mediators, and improved clearance of lipids from the serum. Animal studies have shown that IV fat emulsions (IFE), such as fish oil that are high in eicosapentaenic and docosahexaenoic acid, educe impairment of bile flow which is seen in cholestasis caused by conventional fat emulsions (Alwayn, 2005; Van Aerde, 1999). By administering Omegaven™ in place of conventional soybean fat emulsions we hope to reverse or prevent the progression of PNALD, allowing sufficient time for intestinal rehabilitation and eventual cessation of parenteral nutrition.

We propose to conduct a prospective evaluation of the use of Omegaven™ for the provision of parenteral lipid calories in concert with an active ongoing program of intestinal rehabilitation. Our main outcome of interest will be need for small bowel transplantation, with secondary outcomes including improvement in clinical measures associated with PNALD and need for liver transplantation. This study will be conducted in both pediatric and adult intestinal rehabilitation patients.

## STUDY PROTOCOL

### Hypothesis

Established parenteral nutrition (PN) associated liver disease can be reversed or its progression halted by using a parenteral fat emulsion prepared from fish oil as measured by normalization of serum levels of hepatic enzymes and bilirubin.

### Objectives

The primary objective of this study is to evaluate the need for small bowel transplantation. Clinical data will be collected prospectively and will be compared with historical controls.

Secondary objectives are to determine if there are improvements in clinical measures associated with established parenteral nutrition- associated liver disease (PNALD).

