### Efficacy and Safety Variables

The efficacy and safety variables in this study will be the change from the baseline assessment to the end of follow-up assessment or end of treatment assessment for the variables listed below. The variables will be determined from: the measurement of body weight, the recording of TPN prescriptions, blood and urine analyses, radiology reports, GI exams, and possible liver biopsies.

- Parenteral Nutrient Requirements (determined from the TPN/PN prescription)
  - TPN/PN infusions (days/week)
  - TPN/PN fluid volume (cc/week)
  - TPN calories (kcal/week)
  - TPN protein (g/week)
  - TPN lipid (g/week)
  - Intravenous vitamins (type and # of infusions/week)
  - Intravenous trace elements (type and # of infusions/week)
  
- Assessment of Nutritional Status
  - Body Composition
  - Body Weight
  
  - Nutrient and Metabolic Profile (Blood analyses)
  - Vitamins- A, B12, C, D, E, folate
  - Minerals and trace elements - calcium, phosphorus, iron, selenium, zinc
  - Serum Proteins - total protein, albumin, globulin
  - Lipid profile - essential fatty acids levels
  - Citrulline, D-lactic acid
  - Serum Electrolytes – (sodium, potassium, chloride, bicarbonate, magnesium)
  
- Assessment of Hydration Status/ Renal Function (Blood analyses)
  - Blood urea nitrogen
  - Serum creatinine

- Assessment of Liver Function (Blood analyses)  
Total bilirubin, direct and indirect bilirubin, alkaline phosphatase, SGOT, SGPT, LDH.
- Assessment of Upper and Lower GI tract/Liver  
Upper and Lower endoscopy, mucosal biopsies and bacterial cultures  
Ultrasound of abdomen/Small bowel follow through, Barium enema  
Liver biopsy (based on clinical indication)

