## **Study Design**

This study will be a prospective, non-randomized, open-label study of Omegaven™ with a total enrollment of 100 patients, for provision of parenteral lipid calories. The study cohort, receiving the PN at 1g/kg/day, will be compared to historical controls at UNMC where parenteral lipid calories were provided exclusively through soybean-based formulations, as well as, assessing the study cohorts need for small bowel and liver transplantation.

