#### **3. Treatment**

The Treatment Period will not begin until the patient undergoes a full initial evaluation. Informed consent will be obtained before treatment is initiated. After the initial evaluation is complete and inclusion criteria are found to be met, therapy with Omegaven™ will be initiated at the goal dose of 1 gram per kilogram per day, over 12-24 hours. Omegaven™ will be infused intravenously through either a central or peripheral catheter alone or in conjunction with parenteral nutrition. If additional fat calories are needed, they will be provided via the central route. The same standards of care provided to all patients receiving parenteral nutrition solution will be followed, with routine nutritional monitoring.

In the event that a patient is unable to achieve adequate calories parenterally and is unable to tolerate enteral feeds, it may be necessary to evaluate whether or not the patient should continue the study with Omegaven™ or resume therapy with the conventional fat

emulsions so that additional parenteral fat calories can be given. The clinical team will determine if the patient should be removed from the protocol, and the IRB and FDA will be notified.

Orders for Omegaven™ will contain the following data elements;

- Total daily dose to administered in mL
- The hourly infusion rate (total daily dose ÷ the number of hours to be infused)

Prior to the administration of each Omegaven™ dose, two nurses will check the dose dispensed against the physician's orders and verify that the infusion pump settings (hourly rate, volume to be infused) are correct before the infusion is started.

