## **Inclusion Criteria**

The first 100 eligible patients must meet the conditions listed below:

- Patients must be enrolled in the Intestinal Rehabilitation Program at the University of Nebraska Medical Center, and:
- Be unable to meet nutritional needs solely by enteral nutrition and be expected to require PN for at least another 30 days
- Have clinical evidence of parenteral nutrition associated liver disease (PNALD) as defined as direct bilirubin of 2mg/dl or more. A liver biopsy is not necessary for treatment.
- Signed patient informed consent.

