### **Duration of Therapy**

Patients will remain on Omegaven™ until weaned from PN and may continue monotherapy with Omegaven™ as an additional source of calories after the dextrose/protein portion of PN is discontinued.

In the event that a patient is listed for a liver or liver/intestinal transplant and an organ becomes available, the participation in this protocol will not preclude them from receiving the transplant.

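### The primary objective, need for small bowel transplantation, has no definition, time point or assigned between-group analysis, although a general comparison with historical controls is intended

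*Combined protocol and SAP*

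**What the plan says.** Two sections name the outcome. Background and Rationale says "Our main outcome of interest will be need for small bowel transplantation", with need for liver transplantation among the secondary outcomes. Objectives says "The primary objective of this study is to evaluate the need for small bowel transplantation", and its next sentence announces a comparison of the clinical data with historical controls. Study Design adds, next to the control comparison, "assessing the study cohorts need for small bowel and liver transplantation".

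Other sections point elsewhere. Hypothesis measures success by normalisation of liver enzymes and bilirubin. Efficacy and Safety Variables begins "The efficacy and safety variables in this study will be the change from the baseline assessment" and applies this to a list of nutritional, laboratory, radiological and endoscopic variables. Transplantation is not on that list, nor in the assessment lists for the evaluation, treatment, outpatient and follow-up periods.

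Statistical Analysis gives a two-group comparison, four frequency-matching factors and a 0.05 threshold. It assigns repeated-measures ANOVA to changes between assessments, Fisher's exact test to adverse events, and univariate and multivariate analysis to baseline factors that may affect an unnamed outcome.

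**The concern.** A primary objective can be tested only if the plan says which event counts, by when, measured from what date, and compared how. None of these is fixed here. *Need* could mean listing, transplant performed or a clinical judgement. Duration of Therapy covers the case "In the event that a patient is listed for a liver or liver/intestinal transplant and an organ becomes available", but nothing says whether a combined graft counts towards the primary small bowel outcome, the secondary liver outcome, or both.

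The study is open-label and non-randomised, and its controls are past patients of the same centre. Whoever settles these choices later may already know how the controls fared. Neither blinding nor randomisation offsets that freedom, so a result for the main outcome could not be told apart from one reading picked among several.

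**Working it through.** **1. What is fixed and what is not.** The plan states no event rate, effect size, number of controls or power, so there is no figure of its own to reproduce. The main check is of the text.

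| Element | Where it should stand | What is there |
|---|---|---|
| Comparator, matching factors, P<0.05 | Objectives; Statistical Analysis | Present |
| Meaning of *need*; combined grafts | Objectives; Efficacy and Safety Variables | Absent |
| Time point | Efficacy and Safety Variables | End of follow-up or end of treatment, for the listed variables only |
| Data collection | Assessment lists | Transplant not listed |
| Between-group test | Statistical Analysis | None assigned to transplant |
| Cohort follow-up | Discontinuation of Therapy (dosing part) | Open-ended, to a clinical state |
| Control follow-up, data cut-off | Anywhere | Not stated |

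**2. If Fisher's test is borrowed for crude proportions.** Everything from here on is illustration. Assumed: 100 versus 100 patients, identical true transplant hazards, two-sided test at 0.05. With transplant hazard *h* and combined weaning/death hazard *c*, the proportion transplanted by time *t* is

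h/(h+c) × (1 − exp(−(h+c)t)).

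Example: h = 0.10 and c = 0 give 1 − exp(−0.1) = 9.5% at 1 year and 1 − exp(−0.2) = 18.1% at 2 years. Exact enumeration of all 101 × 101 tables gives the chance of a significant difference with 1 year of follow-up in one group and 2 years in the other:

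| c per year | h=0.10 | 0.15 | 0.20 | 0.25 |
|---|---|---|---|---|
| 0 | 35.6% | 50.1% | 61.8% | 70.9% |
| 0.5 | 11.4% | 16.7% | 20.6% | 24.0% |
| 1.0 | 5.0% | 6.5% | 8.0% | 9.0% |
| 1.5 | 2.9% | 3.7% | 4.2% | 4.8% |

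With 1 year in both groups the rate is 2.1–3.3% throughout. Swapping the groups gives the same rates in the opposite direction.

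**3. Unequal deaths, equal follow-up.** With death hazards of 0.3 versus 0.1 per year and 3 years of follow-up, the rate is 10.9–24.6% with no weaning, 5.0–8.0% at weaning 0.5 per year and 3.3–4.8% at 1.0 per year. At 12 months it is 2.4–4.2% in all these cases.

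**4. Choosing the reading afterwards, equal follow-up.** Three readings (listed; transplanted; transplanted or died) at 1, 2 or 3 years give nine analyses. Assumed hazards per year: listing 0.3 or 0.6, transplant after listing 0.5 or 1.0, death 0.1, weaning 0.5 or 1.0 (8 scenarios, 20,000 simulated trials each). One fixed reading is significant in 1.1–4.4% of trials, at least one of the three at 12 months in 6.6–8.2%, and at least one of the nine in 12.8–16.6%.

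**5. Events available at a short horizon.** With the control hazards of step 2 and an assumed hazard ratio of 0.5, the expected transplants by 12 months in both groups together are:

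- lowest case (h = 0.10, c = 1.5): 5.0 + 2.5 = 7.5, about 8;
- highest case (h = 0.25, c = 0): 22.1 + 11.8 = 33.9, about 34.

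Schoenfeld's formula for 80% power with 1:1 groups needs 4 × (1.960 + 0.842)² / (ln 0.5)² = 65.3, so 66 events. For a halved transplant proportion, Fisher's test with 100 per group has power 19%, 44% and 67% at control proportions of 10%, 20% and 30%.

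**The case against.** The strongest reply is that the comparison is plainly intended. The sentence after the primary objective says so, the Abstract repeats it, and Statistical Analysis opens with the two groups. This stands. A reader might infer from the Study Design wording, which speaks only of the cohort's need, that it is unsettled whether transplantation is compared at all. Read with Objectives, the documents do not support that. What is missing is the method, not the intent.

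The reply continues that Fisher's test is the obvious choice and that transplants will be in the charts. Both may be true, but the plan ties Fisher's test to adverse events, and having charts does not settle which event, by when, or from what date.

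It is also fair that the large percentages rest wholly on assumptions. Weaning is the hoped-for way out (Background and Rationale: "allowing sufficient time for intestinal rehabilitation and eventual cessation of parenteral nutrition"), and the rates shrink as weaning rises. If both groups were followed to resolution, a crude proportion could be interpreted, though it would still count a death as no transplant. The inflation in step 4 comes from selective choice; any one fixed reading keeps its level.

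Lastly, an elaborate time-to-event model at 12 months is not needed to close the gap and, with about 8–34 events, could hardly carry the matching factors. That stands too and limits the fix.

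**Conclusion.** The point holds and must be fixed. Followed as written, the plan has no prespecified between-group analysis for its own primary objective. This rests on the text alone and on no assumed rate.

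The consequences are conditional. A crude proportion favours whichever group has the shorter follow-up or more deaths. A reader might infer that the bias favours Omegaven, or that false-positive rates of 36–71% are to be expected. The documents support neither: they give no transplant, death or weaning rates, no number of controls and no control follow-up. On the assumptions shown, unequal follow-up can matter greatly or hardly at all, and the direction is unknown.

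**What to change.** Amend Efficacy and Safety Variables and Statistical Analysis as follows.

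1. **Endpoint.** Small bowel transplant performed, alone or in a combined liver/intestinal graft, within one common horizon from an index date defined the same way in both groups. The date the entry criteria were first met is one candidate. For controls, the criterion "be expected to require PN for at least another 30 days" then needs a stated rule for chart review. In the cohort, "The Treatment Period will not begin until the patient undergoes a full initial evaluation", so the plan should also say how the time between index date and first infusion is treated. Choose the horizon in advance and long enough for a usable number of events; step 5 suggests that 12 months may be too short.
2. **Data.** Take transplant, listing, death and PN-weaning dates from the charts in both groups.
3. **Analysis.** Name one primary between-group test at that horizon, with its sidedness, and keep it simple given the few events expected. Fisher's test on the proportion transplanted by the horizon would serve if status is known for everyone. State how death before transplant and incomplete follow-up are handled.
4. **Support.** Report transplant-free survival, so that deaths cannot pass as a benefit.

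Settle this before the control outcomes are abstracted. Because the controls come from the same centre, some outcomes may already be known; prespecification reduces that risk but does not remove it.

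The cost is protocol wording, chart abstraction, and some precision lost by discarding events after the horizon. No extra patients or procedures are needed.

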### **Discontinuation of Therapy –**

- In the event that a patient is unable to achieve adequate calories parenterally and is unable to tolerate enteral feeds, it may be necessary to evaluate whether or not the patient should continue the study with Omegaven™ as monotherapy or resume therapy with conventional fat emulsions so that additional parenteral fat calories can be given.
- Adverse Event (AE) – Any patient with anaphylactic or allergic reactions to Omegaven™ will not continue treatment and will be withdrawn from the protocol.
- Inter-current Illness – If a patient develops an illness during the course of the study that is not associated with the condition under study and that requires treatment inconsistent with the protocol requirements (such as an interruption of regular participation in the study), the patient may be discontinued from further participation in the study. A patient may also be discontinued from the study if he develops an inter-current illness or complication that in any way justifies his withdrawal from the study. However, if an inter-current illness develops which can be managed without significant interference with the requirements of the protocol, the patient need not be discontinued.
- The patient will complete treatment with Omegaven™ in this study when he/she is completely off PN, develops a contraindication for further use, or the patient/family requests to be removed from the study.

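### The transplant outcome has no rule for death before transplant, so a group's result can look better because more of its patients died, or a survival benefit can be hidden

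*Combined protocol and SAP*

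**What the plan says.** Under Objectives: "The primary objective of this study is to evaluate the need for small bowel transplantation". Background and Rationale agrees: "Our main outcome of interest will be need for small bowel transplantation". The secondary outcomes named there are measures of the liver disease and the need for a liver transplant. Under Study Design the trial is open-label and non-randomized, "with a total enrollment of 100 patients", and is compared with historical controls from the same centre. The number of controls is not given.

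Efficacy and Safety Variables begins: "The efficacy and safety variables in this study will be the change from the baseline assessment to the end of follow-up assessment". An assessment when treatment ends may serve instead. The list that follows covers parenteral nutrition, nutritional status, renal and liver tests, and GI and liver examinations. Neither transplant nor death is on it.

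Under Patient Discontinuation, the completion rule reads "The patient will complete treatment with Omegaven™ in this study when he/she is completely off PN, develops a contraindication for further use". A request by the patient or family to leave is the remaining reason. Death is not among the reasons.

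Statistical Analysis provides a two-way repeated-measures ANOVA, Fisher's exact test for adverse events, and univariate and multivariate analyses that are not described further. It has no time-to-event method, no competing-event method, no composite, and no rule for a patient who dies before transplant. The nearest provision is in Treatment/Follow-up Period, where adverse experiences are to be recorded for every patient during enrolment.

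**The concern.** Patients enter with established liver disease (direct bilirubin of 2 mg/dl or more, Inclusion Criteria). Background and Rationale says that progression of this disease limits patients whose bowel could otherwise be rehabilitated. Duration of Therapy foresees patients who are listed and waiting for an organ. Death before transplant is therefore foreseeable, and it makes transplant impossible.

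Treatment is meant to halt or reverse the liver disease and so give the bowel time to recover. A lower transplant count could mean that this worked, or that more patients died before an organ was offered. The primary outcome cannot separate the two. If instead Omegaven lowers mortality, more patients survive long enough to be transplanted, and a real benefit may be hidden or look like harm.

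The historical comparison adds to the problem. Matching covers gender, age, etiology and severity of liver disease, but not calendar period. Any difference in mortality between the two periods would pass into the transplant comparison. The documents do not say whether there is one.

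**Working it through.** **No figure to reproduce.** The protocol states 100 treated patients without power, effect size, transplant rate, death rate or number of controls. Everything below is illustrative. Only the 100 treated patients come from the documents; the 100 controls and all event counts and rates are assumed.

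**Check 1: same transplant counts, different deaths.** Transplants are fixed at 20/100 on Omegaven and 35/100 in controls. Two-sided Fisher's exact test on transplant alone: P=0.026, an apparent benefit. Transplant-or-death in each group = transplants + deaths without transplant.

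| Deaths without transplant, Omegaven v control | Transplant or death | Fisher P |
|---|---|---|
| 15 v 5 | 20+15=35 v 35+5=40 | 0.56 |
| 10 v 5 | 20+10=30 v 35+5=40 | 0.18 |
| 5 v 5 | 20+5=25 v 35+5=40 | 0.034 |
| 10 v 10 | 20+10=30 v 35+10=45 | 0.041 |
| 5 v 15 | 20+5=25 v 35+15=50 | 0.0004 |

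The transplant-only result is the same in all five rows. Transplant-or-death is no longer significant when Omegaven deaths exceed control deaths (first two rows). It remains significant when deaths are equal, and is stronger when Omegaven has fewer.

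**Check 2: direction, with the tendency to be transplanted held equal.** Assume constant hazards, a transplant hazard t=0.5/year in both groups, follow-up T=2 years, and a death hazard d that differs between groups.

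- Proportion transplanted = t/(t+d) × (1 − exp(−(t+d)T)).
- Proportion transplanted or dead = 1 − exp(−(t+d)T).

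| d per year | Transplanted | Transplanted or dead |
|---|---|---|
| 0.1 | 0.5/0.6 × (1 − e^−1.2) = 58% | 70% |
| 0.3 | 0.5/0.8 × (1 − e^−1.6) = 50% | 80% |
| 0.5 | 0.5/1.0 × (1 − e^−2.0) = 43% | 86% |
| 0.8 | 0.5/1.3 × (1 − e^−2.6) = 36% | 93% |

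As deaths rise, the transplanted proportion falls although the transplant hazard has not changed. Compared with a group at d=0.1, with 100 per group and two-sided 0.05, the chance of a significant transplant result favouring the group with more deaths is about 22%, 57% and 90% for d=0.3, 0.5 and 0.8. This holds whichever group has the higher mortality.

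**The case against.** **Need is not the same as receipt.** A reader might infer that the protocol counts every death as no transplant. It does not say so. Need is undefined, and if it means listing or meeting transplant criteria, a patient who dies after that point counts as needing one. This stands, and it narrows the point: under a listing definition only deaths before listing are lost. It does not remove it, because no definition or rule is given.

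**No transplant comparison is specified.** This is also correct. Statistical Analysis names no method for the primary outcome, and the outcome has no time horizon. The handling of death belongs with those gaps and can be repaired with them. However, defining need and choosing a test would not settle what happens to patients who die first.

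**Deaths will be recorded as adverse experiences.** Probably so in the treated cohort, and adverse-event incidence is to be compared between groups. But death is not named there, and an adverse-event table is not joined to the transplant result.

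**Change-from-baseline measures.** A reader might infer that these would exist only for survivors. The documents do not support that. An end-of-treatment assessment is allowed and laboratory tests are drawn about weekly, so patients who die can have post-baseline values. The protocol does not say how such values are used.

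**The illustration can be chosen to give any answer.** This stands. A reader might infer from the 15 v 5 row that the transplant result would be overturned. The documents give no death rates, and with equal or fewer Omegaven deaths in these examples the conclusion does not change.

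**Conclusion.** The concern holds in this form: the primary comparison has no provision for death before transplant, so, made as a simple comparison of transplants, it can favour the group with more deaths or conceal a survival benefit. The absence of death from the objectives, variables, completion rules and analysis can be verified in the text. The direction and size in this trial cannot be known from the documents. With the assumed figures, the same transplant result (P=0.026) goes with transplant-or-death P values from 0.0004 to 0.56. The conclusion assumes that some patients die before transplant (before listing, if need means listing) and that mortality may differ between the cohort and the historical controls. The gap affects the main conclusion of the study and should be closed before the comparison is made.

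**What to change.** 1. In Efficacy and Safety Variables, add all-cause death with its date, collected for both the Omegaven cohort and the historical controls.
2. In Statistical Analysis, compare transplant by cumulative incidence with death before transplant as a competing event. Start from an index date defined the same way in both groups and run to a common time horizon. State what need means, so that it is clear which deaths come before the event.
3. Report transplant-or-death, and each component separately, beside that comparison. State in advance that no transplant benefit will be claimed unless transplant-or-death supports it.

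The cost is a change of wording, one added data item, and follow-up of vital status. The last takes some effort, because patients go back to their referring physicians and a death at home may not be in the centre's records. The composite also includes deaths unrelated to liver disease; showing the components separately helps the reader judge what drives it. No treatment or clinical rule is affected.
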